1. Blinding Plan: This is a double-blind study whereby the investigators, research assistants, research nurse and participants will be blinded as to the drug treatment designation. Once participants have been assessed for eligibility and enrolled in the study, they will be randomized into 1 of 3 different groups. Participants randomized to either group I or II will be blinded to the intervention fantibiotic instillation in group I or placebo (saline alone) in group II]. Gentamicin sulfate will be prescribed for the research participants by the study physician or nurse practitioner and instilled under the direction of the research nurse. Thus, the participants in groups I and II will not be able to discern their assigned treatment. To ensure the double-blind, only the study physician or nurse practitioner as well as the pharmacy, all of whom are not associated with the data collection or data analysis, will be un-blinded. Note, the research nurse assisting participants with the instillation will be blinded. All participants will be identified by number and the instillation solutions (gentamicin or placebo) will be numbered with the pharmacy having access to the code specifying which instillations are active and which are placebo for each participant. The investigators and direct research team members will not be permitted to have knowledge of the group assignments. In the case of a drug related adverse event, the study physicians will evaluate the event and prescribe treatment that will minimize or completely resolve the event if minor or moderate in severity and it does not interfere with activities of daily living or quality of life (as determined by the participant). Should it be determined that the event has gotten worse, or if the participant can no longer tolerate the event, the study drug will be discontinued, and the participant will be terminated from study participation. There are no expected reasons to unmask the study treatment. The study physician or nurse practitioner will decide if the blind is to be broken or not. The blind will not "routinely" be broken when a serious adverse event (SAE) occurs. If an SAE is probably or definitely drug-related, the drug/placebo intervention will be stopped, and the participant treated appropriately. Emergency drug code envelopes will be created by the pharmacy at the study site. These will be labeled by participant randomization number and contain information, which will un-blind the treatment of the individual subject. These envelopes are to be used only in extreme emergencies, such as when an emergency situation exists in which the participant's treatment would be affected by knowledge of his drug therapy, and there is no time to contact the Medical Monitor. Note, that at the end of the study, participants will be un-blinded to the intervention designation by the study physician or nurse practitioner. If a participant was randomized to the no instillation group, however, he/she may re-enroll into the study and directly receive the gentamicin intervention and are not required to wait until the end of study, as all parties are un-blinded and aware of the treatment (standard of care) in this instance. All data from participants re-enrolling into the gentamicin-only group will be kept separate from those who are enrolled in the main study who are blinded.

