
The following participant withdrawal criteria may be implemented in determining when and how to withdraw participants from the trial/investigational product treatment.

Drug Discontinuation Criteria:

The subject's participation may be terminated for safety precautions based on any of the following by the study investigator. 1) Drug-related severe adverse event; 2) UTI requiring intravenous antibiotics; 3) Diagnosis of systemic absorption; 4) Diagnosis of nephrotoxicity; 5) Diagnosis of ototoxicity; 6) Diagnosis of renal failure

Temporary Discontinuation Criteria:

Situations of temporary discontinuation of study drug followed by subsequent resumption of study drug are: 1) Resolution of an adverse event, especially in cases where it is determined that the study drug was unlikely to have caused the event. 2) Resolution of a symptomatic UTI.

Withdrawal from Study:

A participant may withdraw from study participation at any time. Whatever data has been collected at the time of study termination will be evaluated by the PI for use in the final study database. If a participant is terminated from the study, the investigator will have the option to recruit an additional participant. Of withdraw from the study was due to an adverse event, participants will be followed until complete resolution of the adverse event that was possibly or definitely drug-related.

2. Statistical Plan: Data will first be summarized. We will use means with associated standard deviation, median with associated interquartile range and full range (min-max) to summarize continuous variables. Categorical variables will be summarized with frequency count and standard deviation. We will perform 2 types of analyses: pre-post differences within each group and between group comparisons of the differences. To evaluate the pre-post changes in each group, we will use paired t-test. To compare the changes between the 3 groups, we will use ANOVA test. If the ANOVA test yields significant results, we will perform follow-up 2 by 2 group comparisons using 2-sample t-tests. If the underlying assumptions of these tests are not satisfied, we will use the non-parametric equivalent tests instead.

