We propose to use a sample size of 36 (12 in each of the three arms). Cox et al., (46) has found that the use of intravesical gentamicin was associated with a reduction of a median 3 symptomatic UTIs in 6 months in 22 patients. Using the formulas proposed by Hozo et al., (47) we estimated the corresponding standard mean change to be 2.48 with a standard deviation of 1.7. Assuming the same standard deviation in our data, a sample size of 12 achieves 80% power to detect a mean of paired differences of as low as 1.5 symptomatic UTIs for the gentamicin group with a significance level of 0.05 using a two-sided paired ttest (48, 49). We expect to observe a drop of at least 2 symptomatic UTIs in 6 months. With the same setting, i.e. SD = 1.7, a sample size of 12 achieves 97% power to detect that. Our study will compare changes between the gentamicin instillation, the saline instillation and the no-instillation groups. We will use the comparison between the gentamicin and the non-instillation group to estimate the power. The estimated effect of gentamicin is a reduction in symptomatic UTIs of 2 with a standard deviation of 1.7 (described above) and we assume no change for the non-instillation group (mean reduction of 0 with a standard deviation of 0). With these values, sample sizes of 12 (gentamicin) and 12 (no-instillation) achieve 96% power to reject the null hypothesis of equal means with a significance level of 0.050 using a two-sided two-sample unequal-variance t-test (48-51). The power analysis was performed in PASS 14 Power Analysis and Sample Size Software (NCSS, LLC. Kaysville, Utah, USA, ncss.com/software/pass).

Experimental Outcomes – Research Procedures

1. Intravesical Gentamicin Sulfate Instillation

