
8. International SCI Data Sets

The International SCI Urinary Tract Infection data set (32) will be used to standardize the collection and reporting of information related to possible UTIs and includes such variables as: date of data collection, length of time of sign(s)/symptom(s), results of urine dipstick test for nitrite and leukocyte esterase, urine culture results and resistance pattern. This data set will be completed by the researcher(s). It will also be

used in combination with the International SCI Lower Urinary Tract Function Basic Data Set (Version 2), which contains information on the bladder-emptying method(s), urinary incontinence and any medications usage (59). The latter data set will be conducted by the researcher(s) with the participant.

D. Limitations

A limitation of this study will be the variable nature of the host urinary microbiome. Conventional thought has been that we all are colonized with similar organisms and thus, we should have similar responses to treatment interventions. However, through the Human Microbiome Project (60), we have learned that each of us have diverse microbial communities present in the gut, skin, and vagina (bladder was not investigated) and may help explain why some individuals benefit more from a particular treatment or are more susceptible to infections than others. Our approach in this study is to investigate the effects of a focused, placebo-controlled intervention in a specific population. In doing so, the results from this project may help differentiate responders from non-responders and can be integrated with current studies in the lab assessing the urinary proteome.

III. Human Subjects

There are approximately 1,275,000 Americans with a SCI. Fifty-six percent of the injuries occur in people aged 16 to 30, with an average age of 31, and 82% of the total population are male. Minorities make up 38% of SCI cases, and while every effort will be made to recruit minorities, based on the incidence rates, their participation may be limited. Every effort will be made to recruit women, though only about 18% of SCI patients are female.

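### No between-arm contrast is named as decisive, and the only one with a power figure is gentamicin versus the open no-instillation arm, not the blinded comparison with saline

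*Combined protocol and SAP*

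**What the plan says.** **Aim.** II.A describes a feasibility study, but also says that it will test the efficacy of intravesical gentamicin and study its local pharmacological effect. Saline and no instillation are both listed as controls, without ranking, and Hypotheses 1.1 and 1.2 compare gentamicin with controls in the plural. II.D (Limitations) adds: "Our approach in this study is to investigate the effects of a focused, placebo-controlled intervention in a specific population".

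**Blinding.** II.B and II.B.1 call the three-arm study double-blind, and II.B.1 states: "The investigators and direct research team members will not be permitted to have knowledge of the group assignments". The same section blinds participants only in groups I (gentamicin) and II (saline). It explains why a no-instillation participant may re-enroll early: "as all parties are un-blinded and aware of the treatment (standard of care) in this instance".

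**Procedures.** Saline participants follow the same training and dwell-time progression as gentamicin participants (Research Procedures, item 2). In the no-instillation arm, suprapubic participants are trained in the laboratory and clamp for up to 2 hours (item 3). Participants on intermittent catheterization, 6 of the 12, have no procedure (Figure 2).

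**Analysis.** II.B.2 plans paired tests within arms and a three-group ANOVA of the changes. Then: "If the ANOVA test yields significant results, we will perform follow-up 2 by 2 group comparisons using 2-sample t-tests". No pair is named as primary and no success rule is given.

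**Power.** After a paired calculation for the gentamicin arm, II.B.2 says: "We will use the comparison between the gentamicin and the non-instillation group to estimate the power". The inputs are: "The estimated effect of gentamicin is a reduction in symptomatic UTIs of 2 with a standard deviation of 1.7" and "we assume no change for the non-instillation group (mean reduction of 0 with a standard deviation of 0". The result is 96% with 12 per arm, "with a significance level of 0.050 using a two-sided two-sample unequal-variance t-test". No saline mean, saline SD or power against saline is given.

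**The concern.** The saline arm separates the drug from everything that comes with it. Gentamicin and no instillation differ in the instilled fluid and in knowledge of assignment for everyone, and also in training and dwell for the intermittent-catheterization half. Gentamicin and saline are meant to differ only in the drug.

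A symptomatic UTI requires a participant complaint, so open assignment can affect the count. The plan nevertheless gives between-arm power only for the open comparison and does not say which comparison carries the conclusion. A reader cannot tell whether a win over the open arm alone would count as efficacy, nor how likely the trial is to show a difference from saline.

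**Working it through.** **Inputs from II.B.2:** 12 per arm; mean reduction 2 and SD 1.7 with gentamicin; mean 0 and SD 0 with no instillation; two-sided alpha 0.05. **Assumptions, because the documents give no values:** SD 1.7 in both arms when two arms are compared; saline reduction of 0, 0.5 or 1.0; non-drug shifts of 0.5, 1.0 or 1.5 UTIs. No dropout allowance is applied.

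**Step 1: reproduce the 96%.** The standard error is √(1.7²/12 + 0²/12) = 0.491. The noncentrality is 2/0.491 = 4.08. The Welch degrees of freedom are 11, so the critical t is 2.201. Power from the noncentral t is 95.9%, in agreement with the plan. With a control SD of 0, this is arithmetically the same as a paired test in the gentamicin arm alone, so the control arm adds no uncertainty.

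**Step 2: the same open contrast with SD 1.7 in both arms.** The standard error is 1.7 × √(2/12) = 0.694. The noncentrality is 2/0.694 = 2.88, with 22 degrees of freedom and critical t 2.074. Power is 78.6%. The fall from 96% to 79% comes from replacing the SD of 0, not from the choice of contrast.

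**Step 3: gentamicin versus saline, 12 per arm, SD 1.7 in both.** Noncentrality = (2 − saline reduction)/0.694. The gated column requires a significant ANOVA first (simulated, with no change in the open arm).

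| Saline reduction | Difference | Noncentrality | Power | Power after ANOVA gate | n per arm for 80% (ungated) |
|---|---|---|---|---|---|
| 0 | 2.0 | 2.88 | 79% | 74% | 13 |
| 0.5 | 1.5 | 2.16 | 54% | 51% | 22 |
| 1.0 | 1.0 | 1.44 | 28% | 26–27% | 47 |

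The smallest difference detectable with 80% power at 12 per arm is 2.03 UTIs.

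**Step 4: no drug effect.** Simulated three-arm trials with gentamicin truly equal to saline, both shifted from the open arm by a non-drug amount, SD 1.7 throughout:

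| Non-drug shift | Gentamicin vs no instillation, ungated | Same, after ANOVA gate | Gentamicin vs saline, after ANOVA gate |
|---|---|---|---|
| 0.5 | 11% | 6% | 3% |
| 1.0 | 28% | 20% | 4% |
| 1.5 | 54% | 46% | 5% |

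Only the comparison with saline keeps the chance of a false drug claim at or below 5% in every row.

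**The case against.** A reader might infer that the plan intends to interpret the trial through gentamicin versus no instillation, or that any significant pair would count as success. The documents support neither. II.B.2 uses that contrast only to estimate power, straight after saying that all three groups will be compared, and the follow-up tests include gentamicin versus saline. No success rule is written, and controls in the plural could equally mean that both must be beaten. What stands is the ambiguity and the missing power figure. It is also too much to say that this contrast alone sized the trial, since 12 per arm is first justified by the paired test.

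Further points have weight:

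- **Arm differences.** The suprapubic half of the open arm does get training and clamping up to 2 hours. The training-and-dwell argument therefore applies fully only to the other half.
- **Endpoint.** Item 4 of the Research Procedures adds urinalysis or microscopy and culture criteria to the complaint, and excludes smell or cloudiness alone. The outcomes of Hypothesis 1.2 are measured at cystometry. Both limit reporting bias. For UTI counts the limit is partial, because I.D says that catheter use itself leads to colonization and, in the IDSA guideline text, that pyuria should not separate colonization from infection.
- **Simulation.** The shifts in step 4 are assumed. The simulation shows what would follow from them, not that they exist.
- **Feasibility.** The label softens the consequences, but the same section claims an efficacy test.

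**Conclusion.** The point holds as a gap in specification and should be fixed. The plan names no decisive between-arm contrast. Its 96% belongs to the open comparison under a control SD of 0, and the one blinded, procedure-matched comparison has no power statement. With SD 1.7 in both arms, its power at 12 per arm is about 79% if saline does nothing, and 54% or 28% if saline itself lowers UTIs by 0.5 or 1.0, slightly lower after the ANOVA gate.

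A reader might take the fall from 96% to 79% as the price of moving to saline. It is not: the open contrast falls to the same 79% once its SD of 0 is replaced. Only the further fall to 54% or 28% reflects a saline effect, whose size the documents do not give.

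The match between the two instillation arms also depends on an unresolved text: item 1 of the Research Procedures mentions both 50 ml and 60 ml syringes for gentamicin, item 2 a 50 ml syringe for saline, and Figure 2 gives 60 ml for both.

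**What to change.** - **II.B (Hypotheses 1.1 and 1.2, in II.A, included) and II.B.2, analysis:** state that any claim of gentamicin efficacy rests on gentamicin versus saline. Make gentamicin versus no instillation secondary, described as the open-label effect of the whole instillation package. Present saline versus no instillation as the estimate of the non-drug part.
- **II.B and II.B.1:** limit the double-blind label to groups I and II, and reconcile the statement that the research team will not know assignments with the open third arm.
- **II.B.2, sample size:** give power for gentamicin versus saline at 12 per arm, with the assumed saline change and SD stated and a range such as that in step 3. Replace the control SD of 0 if the open contrast is still reported.
- **Research Procedures items 1 and 2, and Figure 2:** reconcile the syringe and volume descriptions.

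The arms, visits and enrolment do not change. The cost is a less favourable stated power. If saline has a real effect, the plan would have to acknowledge that 12 per arm may be too few for the drug question: 80% power would need 22 or 47 per arm for a saline reduction of 0.5 or 1.0.

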University of Louisville Hospital and Frazier Rehab Institute evaluates approximately 300 chronic SCI outpatients each year. We also have a database of over 5,000 people with SCI who have expressed interest in participating in our research programs. We will select individuals to assure that there is a minimum of 25% women to adequately represent the percentage in the SCI population.

All SCI research participants, irrespective of gender, will be selected based on the following:

Inclusion Criteria

- At least 18 years of age;
- Non-progressive spinal cord injury;
- Stable medical condition;
- Bladder dysfunction as a result of spinal cord injury
- History of recurrent UTIs (defined as 3 or more within the past year or 2 or more within the past 6 months).

Exclusion Criteria

- Signs or symptoms of serious UTI that requires the use of systemic antibiotics;
- Use of any urine-acidifying agent, bladder irrigant, or systemic antibiotic within the previous 2 weeks;
- Participants colonized with gentamicin-resistant bacteria on baseline urine culture or a gentamicin allergy/sensitivity;
- Participants with known hearing loss and/or renal disease;
- Pregnant at the time of enrollment or planning to become pregnant during the time course of the study.

A. Screening and Enrollment

Potential research participants will be identified by our research database (UofL IRB 06.0647) and contacted by research staff prioritized by the initial date they entered the database and provided with general information regarding the research study. If the individual is interested in learning more about the study, the clinical coordinator will set up an info session via teleconference or a meeting at Frazier Rehab Institute. The designated project leader and clinical coordinator will attend the info session and the project leaders (Drs. [name] and [name]) will describe the project including the time commitment, the general design of the study, the interventions and the randomization process. Specific questions from the potential research participant will be answered.

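### The 96% power for gentamicin versus no instillation rests on a control-group SD of 0; with SD 1.7 in both arms it is about 79%

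*Combined protocol and SAP*

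**What the plan says.** Section II.B.2 of the combined protocol and SAP sets the sample size: "We propose to use a sample size of 36 (12 in each of the three arms" each compared on pre-post change in symptomatic UTIs.

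The SD comes from a published gentamicin series of 22 patients. From its reported median the plan derives a mean and SD: "we estimated the corresponding standard mean change to be 2.48 with a standard deviation of 1.7". It carries the 1.7 into its own paired-test calculations for the gentamicin arm (80% power for a drop of 1.5, 97% for a drop of 2).

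For the between-group comparison it says: "We will use the comparison between the gentamicin and the non-instillation group to estimate the power". The gentamicin input is "The estimated effect of gentamicin is a reduction in symptomatic UTIs of 2 with a standard deviation of 1.7". For the control arm, "we assume no change for the non-instillation group (mean reduction of 0 with a standard deviation of 0". With these inputs, 12 and 12 participants "achieve 96% power to reject the null hypothesis of equal means with a significance level of 0.050 using a two-sided two-sample unequal-variance t-test".

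The analysis described earlier in the same section is not a single pairwise test. The three groups are first compared by ANOVA, and then: "If the ANOVA test yields significant results, we will perform follow-up 2 by 2 group comparisons using 2-sample t-tests".

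**The concern.** A mean change of zero without treatment is a defensible assumption. An SD of zero is a different claim: that every untreated participant has the same change. Entry requires "History of recurrent UTIs (defined as 3 or more within the past year or 2 or more within the past 6 months", and episode counts in such people vary from one period to the next by chance alone. The plan gives no reason for the zero and no sensitivity analysis.

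Setting the SD to 0 removes the control arm's sampling variation, so what is labelled a two-sample calculation carries no between-group uncertainty. Yet Hypothesis 1.1 is comparative: it is about gentamicin against controls. A reader who accepts 96% puts the chance of missing a true difference of 2 at 1 in 25, and could take a null result as strong evidence against such a benefit.

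**Working it through.** **Inputs, all from section II.B.2.** n = 12 per arm; difference in mean change 2; gentamicin SD 1.7; control SD 0 as stated; two-sided alpha 0.05; unequal-variance (Welch) t-test.

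**Formulas.** SE = √(s₁²/n + s₂²/n). Welch df = (s₁²/n + s₂²/n)² / [(s₁²/n)²/(n−1) + (s₂²/n)²/(n−1)]. Noncentrality = difference / SE. Power is the probability that a noncentral t with that df and noncentrality falls outside the two-sided 5% critical values.

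**1. The plan's figure.** With SDs 1.7 and 0:
- SE = 1.7/√12 = 0.491
- df = 11
- noncentrality = 2/0.491 = 4.08
- power = 95.9%, which reproduces the stated 96%

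These are the df and noncentrality of a one-sample paired t-test on the gentamicin arm alone. The exact power of that paired test is therefore also 95.9% (the plan states 97% for it). The between-group figure adds nothing to the paired one.

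**2. SD 1.7 in both arms.**
- SE = 1.7 × √(2/12) = 0.694
- df = 22
- noncentrality = 2/0.694 = 2.88
- power = 78.6%

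A simulation of the Welch test (200,000 trials) gives 78.2%; the normal approximation gives 82.2%.

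**3. Range of control SDs** (gentamicin SD 1.7, difference 2, 12 per arm):

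| Control SD | Power |
|---|---|
| 0 | 95.9% |
| 0.5 | 95.0% |
| 1.0 | 91.3% |
| 1.5 | 83.1% |
| 1.7 | 78.6% |
| 2.0 | 71.2% |

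As a guide to plausible values, assume Poisson counts at a constant rate in both periods. The variance of a pre-post difference is then twice the expected count. At the entry minimum of 3 per year (1.5 per 6 months) the SD is √(1.5 + 1.5) = 1.73; at 2 per 6 months it is √(2 + 2) = 2.0. The Poisson model is an assumption, and the entry criteria are minimum histories rather than expected rates.

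**4. The ANOVA step.** With SD 1.7 in all three arms, simulated power to pass the ANOVA and then find gentamicin different from no instillation, for mean reductions in the order gentamicin, saline, no instillation:

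| Means | Gentamicin vs none | Gentamicin vs saline |
|---|---|---|
| 2, 0, 0 | 74% | 74% |
| 2, 0.5, 0 | 70% | 51% |
| 2, 1, 0 | 68% | 27% |

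The plan gives no saline effect, so the second and third rows are illustrations.

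**5. What the design can detect.** With SD 1.7 in both arms and 12 per arm, the single pairwise test has 80% power for a difference of 2.03 and 96% power for 2.70. For a difference of 2, 80% power needs 13 per arm (82.1%) and 96% needs 21 per arm (96.1%).

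**The case against.** The strongest reply is that nothing was miscalculated. The 96% is right for its inputs, and the zero SD is stated openly. That stands: the fault lies in the assumption.

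Second, the 1.7 comes from patients given gentamicin, and the plan never assigns it to untreated participants. That also stands. The 79% is conditional, and a smaller control SD gives more (91% at 1.0). But 1.7 is the only SD of change in the plan, and the Poisson guide puts chance variation alone at about that size. Values near 96% need almost no variation in the control arm.

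Third, the plan expects a drop of at least 2 and derives 2.48 from its source. At 2.48 with SD 1.7 in both arms, pairwise power is 92.7%, and about 91% after the ANOVA if saline is inert. This is true, but the plan attached its 96% to a difference of 2.

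Fourth, the trial is called a feasibility study, and n = 12 is also supported by the paired calculations. Those calculations concern change within the gentamicin arm and say nothing about the comparison with controls. The objectives also say that the study will test efficacy.

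Finally, the scenarios with a saline effect are not in the plan. They show how power falls if saline works; the main conclusion does not depend on them.

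**Conclusion.** The concern holds. The stated 96% depends on a control SD of 0 that is not credible and that nothing else in the documents supports. With SD 1.7 in both arms, a true difference of 2 and no dropout, power is about 79% for the single pairwise test. It is about 74% with the planned ANOVA step and inert saline, and about 68% if saline has half the effect. The chance of missing the planned difference is then roughly 1 in 5 to 1 in 3, against the implied 1 in 25. At 79% the pairwise comparison falls just short of 80%, so this is an overstated figure more than a gross shortfall. The sample-size paragraph should not stand as written.

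**What to change.** In the sample-size paragraph of section II.B.2:

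- Replace the control SD of 0 with 1.7, or with another justified non-zero value, and say where it comes from.
- Delete the 96%. State about 79% for the single pairwise test at SD 1.7 in both arms, with a short table over control SDs (for example 1.0, 1.5, 1.7 and 2.0).
- State power for the analysis as planned, with the ANOVA step: about 74% if saline is inert, and about 68% if it has half the effect.
- Give the difference detectable with 80% power, about 2.0 symptomatic UTIs for the single pairwise test.

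The sample size can stay at 36. The cost is one rewritten paragraph and a less favourable stated power; no participants are added, and treatment and conduct do not change.
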